8. PHARMACEUTICAL INFORMATION

A list of the adverse events and potential risks associated with radiolabeled J591 can be found in Section 7.1.

8.1 Investigational Agent (IND#11,613)

Radiolabeled J591 (¹⁷⁷Lu -J591 and ¹¹¹In-J591) are an investigational agents supplied to investigators by Weill Cornell Medical College. Ketoconazole and hydrocortisone are commercially available and should be prescribed as indicated above (see Section 5.1).

8.2 Radiolabeled J591 Ordering

Upon enrollment, sites will notify the WCMC Study Coordinator of the proposed D29 radiolabeled J591 infusion date. The WCMC Study Coordinator will arrange for shipment of the radiolabeled antibody to the treatment site. After confirmation of the date of infusion at the D15 telephone follow up, the site will confirm treatment date with the WCMC Study Coordinator and shipment to the site's nuclear medicine department will be confirmed.

8.3 Drug Accountability

The case report forms relating to the preparation, quality control and drug accountability will be completed by the radiochemists in nuclear medicine.

Test articles:

- a) mAb HuJ591, 5 mg/ml (non-radioactive, non-DOTA conjugated naked antibody),
- b) DOTA-HuJ591-GS, 8.0 mg/ml (non- radioactive antibody for labeling with ¹⁷⁷Lu)

Storage: The primary inventory of test articles is stored at Goodwin Biotech, Plantation, FL, a cGMP, FDA-approved facility. This storage facility is monitored around the clock and is equipped with back-up power generators in the event of a power outage.

Periodically, as needed, vials of the test articles are shipped to WMC Urologic Oncology where they are stored in a locked, monitored, centrally alarmed refrigerator. Access to the storage area in WMC Urologic Oncology is limited by ID card-required access and a locked refrigerator with a key controlled by the WMC Urologic Oncology Lab administrator ([name]).

Inventory: An official inventory record is kept and updated in real time. On the day of radiolabeling and dose administration to the patient, the radiochemists remove the test articles from the refrigerator and record the number of vials removed from the inventory

and the number remaining in the official inventory record. These records are kept in WMC Urologic Oncology.

The “test article”, ¹⁷⁷Lu-J591, is prepared by the radiochemists in the Nuclear Medicine laboratory. The radionuclides are received and stored in the nuclear medicine department according to the procedures established by the Institutional Radiation Safety Office. The radiolabeling and quality control data on radiochemical purity, immunoreactivity, sterility and pyrogenicity tests are kept in nuclear medicine. Radiolabeled antibody preparations are kept refrigerated until use.

Disposal: Unused radiolabeled antibody preparations are stored in lead containers for decay and subsequently disposed of according to standard radiation safety guidelines. Unused non-radioactive antibody vials and partially used vials (test articles) are destroyed or recycled to the WMC Urologic Oncology research lab for non-clinical research purposes.

9. CORRELATIVE/SPECIAL STUDIES

9.1 Laboratory Correlative Studies

Additional Correlative Tests will be performed during the trial and will be centrally analyzed.

Only the materials (tubes, shipping box, FedEx airbill) for CTC counts via CellSearch methodology will be provided to the site following site activation. Additional materials should be requested directly by emailing [contact]. The site should use their own supplies for the remainder of the tests.

A unique ID (number) for the Adrenal Androgen, CTC, Plasma markers, Archival Tumor, and HAHA samples will be provided by WCMC via email. Please contact [contact] prior to the date of sample collection (if possible) for the unique ID. Please use the number provided to write it on the label and the lab requisition. The material shipment for these samples should be provided by site.

Please notify [contact] when shipping samples, and provide the tracking number. A Requisition form should be completed (as described in the Lab Manual) detailing the samples that are being shipped for all samples except the CTC counts via CellSearch methodology.

Note: Plasma markers (9.1.2) are the only tests that are optional. All other correlative samples are required. The collection of archival tissue may be waived if no tissue is available.

9.1.1 Adrenal Androgen Levels

Serum levels of adrenal androgen levels will be obtained at screening (any time following consent and prior to therapy initiation on C1D1), Cycle 2 Day 1, and at the

time of PSA progression. Collect 10 mL of peripheral blood in a yellow (SST) or red top tube. Label samples with the unique sample number that will be provided by the Weill Cornell Medical College study coordinator to ensure that laboratory personnel will be blinded to subject and clinical data.

Please refer to the Lab Manual for further details on collecting, handling and shipping of adrenal androgen samples.

9.1.2 Plasma markers of hemostatic activation, fibrinolysis, and angiogenesis (optional)

Plasma samples will be collected on C1D1 prior to therapy (may be collected as part of screening within 1 week of C1D1), Cycle 2 Day 1 (prior to J591 administration), Cycle 3 Day 1, at PSA progression, and at end of study. Refer to the Lab Manual for further details on collecting blood samples for plasma markers. Samples will be labeled with a unique sample ID number to ensure that laboratory personnel will be blinded to subject and clinical data.

Refer to the Lab Manual for details on handling and shipping of blood samples for plasma markers.

* Plasma markers are the only tests that are optional.

9.1.3 Circulating tumor cells

Circulating tumor cells (CTCs) will be assessed in the following manner:

- CTC counts via CellSearch methodology
- CTC analysis for research

9.1.3.1 Collection of specimens for CTC counts (enumeration) via CellSearch Methodology:

Kits (including requisition and FedEx airbill) will be provided for CTC samples for counts via CellSearch methodology. At specified time points [baseline C1D1 prior to ketoconazole, C2D1 (prior to Lu-J591), C3D1, at the time of PSA progression, and at end of study] samples for CTC count via CellSearch methodology will be collected. Use the label from the requisition and place it on the tube to ensure that laboratory personnel will be blinded to subject and clinical data. The name should be the unique ID provided by WCMC coordinator (**NOT** the patient name). Refer to the Lab Manual for further details on collecting, handling and shipping of blood samples for CTC counts via CellSearch methodology.

9.1.3.2 Collection of specimens for CTC analysis for research:

At specified time points (screening/baseline at C1D1 prior to treatment and at end of study), blood samples will be collected as described in the Lab Manual. No Kit will be provided for this test, sites should use their own materials. Samples will be labeled

with a unique sample ID number to ensure that laboratory personnel will be blinded to subject and clinical data.

Refer to the Lab Manual for further details on handling and shipping of blood samples for CTC analysis for research.

9.1.3 Human Anti-Humanized Antibody (HAHA) specimen:

Blood samples will be collected at screening and EOS. Refer to the Lab Manual for further details on collecting, handling and shipping of blood samples for HAHA.

9.1.4 Archival Tumor PSMA expression

9.1.4.1 Specimens

At the screening visit, paraffin-embedded tumor blocks or 10 unstained slides with representative tumor tissue will be collected as described in the Lab Manual.

Samples will be labeled with a unique sample ID number to ensure that laboratory personnel will be blinded to subject and clinical data.

For shipping instructions, please refer to the Lab Manual.

9.2 Special Studies

9.2.1 Radiolabeled-J591 Imaging

9.2.1.1 Assessment

9.2.1.1.1 Method of Assessment:

Planar imaging will be performed 2-8 days after radiolabeled-J591 administration (scan window will be assigned at randomization). In the case of a suspicious lesion, SPECT of the area may be performed at the nuclear med physician's discretion. In addition a CT/MRI may be obtained for possible confirmation. Identified sites will be followed on subsequent imaging modalities (bone scan, CT or MRI) to define the interval between identification of the lesion/s by radiolabeled-J591 versus other modalities. Images will be captured as specified in the Imaging Manual and provided to WCMC on disc in dicom format.

9.2.1.1.2 Timing of Assessment

J591 scanning will be performed approximately 2-3 or 6-8 days after J591 administration (scan date will be assigned with randomization). Scans will be assessed centrally at WCMC.

10. STUDY CALENDAR

The study flow chart, including all procedures to be performed during the study, is presented below. Prior to engaging in any study procedure, each patient must sign and date an informed consent form.

Baseline evaluations are to be conducted within *1 week* prior to administration of protocol therapy. Scans and x-rays must be done *within one month* of enrollment (or following enrollment as part of screening).

Study Procedure	Screening Period		V1	V2	V3 ⁸	V4	±	V5	V6	V7	V8	V9	F/U ¹⁴	PSA progression	EOS ¹¹
	Day -28 to -1	C1D1	C2D1	C2 D3-9	C2D22	C3D1	C3D8	C3D15	C3D22	C4D1	Every 4 weeks				
Informed consent	X														
Medical History	X	X ⁺⁺	X ⁺⁺			X ⁺⁺					X ⁺⁺	X ⁺⁺	X ⁺⁺	X ⁺⁺	
Physical Exam (PE)-Complete	X												X	X	
PE – Targeted ⁹		X	X			X					X	X			
Vital Signs ¹⁰	X	X	X ⁺			X					X	X	X	X	
Demographics	X														
Previous Therapy Report	X														
Performance Status	X	X	X			X					X	X	X	X	
Height, weight	X	X	X			X					X	X	X	X	
CBC with differential + platelet count ^{2,3}	X	X	X		±	X	X ³	X ³	X ³	X	X	X	X	X	
PT or INR, PTT	X														
Electrolytes, BUN, Creatinine	X	X	X			X					X	X	X	X	
Total protein, albumin, calcium	X		X			X					X	X	X	X	
total bilirubin, AST	X		X			X					X	X	X	X	
ALT, LDH, Alk Phos	X		X			X					X	X	X	X	
PSA ⁴	X	X	X			X					X	X	X	X	

Testosterone	X									X	X
Urinalysis	X										
Human anti-J591 antibody	X										X
EKG	X										
CT or MRI (abdomen-pelvis) ¹	X								X		
Bone Scan ¹	X								X		
CXR ¹	X								X		
J591 scan				X*							
Adverse Events	X	X	X	X	X			X	X	X	X
FACT-P ¹³		X ¹³							X ¹²	X ¹²	X ¹²
Concomitant Medications	X	X	X		X			X	X	X	X
Concomitant Procedures		X	X		X			X	X	X	X
¹¹¹ In/ ¹⁷⁷ Lu-J591 Administration			X ¹²								
Ketoconazole/Hydrocortisone ⁷		X	X	X	X	X	X	X	X	X	
Plasma Markers		X	X		X					X	X
Circulating Tumor Cells ⁵		X	X		X					X	X
Adrenal Hormones		X ⁶	X ⁶							X ⁶	
Archival Tissue	X										

A phone assessment will be performed on D15 +/- 3 days to assess compliance and toxicity of ketoconazole/hydrocortisone.

± CBC on D50 +/- 2 days is required for pts on anticoagulation or NSAIDS, suggested in pts with baseline plt count < 200

*J591 scan may be done 2-8 days after infusion (date will be assigned upon randomization). SPECT studies of sites of disease will be obtained in selected patients as necessary.

⁺ vital signs to be taken prior to infusion and post-infusion as per Section 5.1.3.3

⁺⁺ interval medical history

¹ Baseline radiographic evaluation should be performed within one month of enrollment (or following enrollment as part of screening). Subsequent scans (CT/MRI abd/pelvis, CXR (or CT chest), and bone scan) should be performed every 6 months until PSA progression, then every three months thereafter unless clinically indicated sooner.

² CBC repeated twice a week when platelets <25,000/mm³ and/or ANC <500/mm³

³ CBC's not associated with study visits may be performed at any CLIA certified laboratory

⁴ The same lab should be used for all study PSA's if possible

⁵ CTC counts via CellSearch (using kit) at C1D1 prior to ketoconazole, C2D1 (prior to Lu-J591), C3D1, at the time of PSA progression, and at end of study. Additional blood samples for CTC analysis for research will be drawn at C1D1 prior to treatment and at end of study

⁶ Adrenal hormone levels should be drawn prior to starting treatment on Cycle 1, Day 1, 1 month, and at PSA progression

⁷ Starting after C1D1 assessment and blood draw until toxicity, investigator, or patient decision as per Sections 5.2.1, 5.2.2, 6.1. Distribute medication diary at the beginning of each cycle.

⁸ Visit 3 (C2D1): Targeted physical exams can be completed the day prior to the scheduled J591 infusion date.

⁹ All references to targeted physical exams throughout the protocol include a heart and lung examination, as well as evaluation of any abnormalities found during the complete physical exam performed at screening

¹⁰ Vital signs include temperature, heart rate, blood pressure, and respiratory rate.

¹¹ The End of Study Visit occurs when patient shows evidence of metastatic disease. Patient remains on trial until documented metastatic disease. In addition to scans a biopsy can be performed to prove metastatic disease. Patient can receive additional therapy prior to showing metastatic disease and still remain on trial. Site will be asked for information regarding the additional therapy in the case report forms.

¹² In the event that the J591 infusion is delayed, cycle 1 will be extended until the date of the J591 infusion. The date of the J591 infusion will be considered Cycle 2, Day 1.

¹³ The FACT-P questionnaire should be completed after enrollment, but prior to therapy (on C1D1 prior to ketoconazole). Questionnaires should also be completed at each radiographic assessment point (q6 months prior to PSA progression, q3 months after PSA progression) – may be performed just prior to scan, on day of scan, or after scan, but BEFORE results of scans are discussed. In addition, FACT-P will be completed at PSA progression and EOS

¹⁴ Follow up is at least every 4 weeks while on ketoconazole and until study drug toxicities have resolved (with the exception of anemia). Following discontinuation of ketoconazole, follow up is at least every 12 weeks (or 3 months)

10.1 STUDY PROCEDURES: Schedule of Events

The assessments to be performed during the study are outlined below by study period, visit and day. Study assessments through Visit 9 (Day 85) will be completed within ± 3 days of the specified day for the visit, except where noted. Visits after Day 169 will be performed within ± 7 days of the scheduled visit.

Screening Period (Visit 1, Days -28 to -1) – All subjects

The procedures outlined for Visit 1 must be completed prior to the patient receiving study drug. The following procedures will be conducted at Visit 1:

- Informed Consent
- Medical History
- Concurrent medications
- Complete Physical Exam
- Vital Signs
- Demographics
- Previous therapy
 - Surgical report will include date and type of surgery +/- lymphadenectomy
 - Radiotherapy report will include modality of therapy with prescribed dose and field and dates of therapy
 - Previous hormonal therapy – drugs, doses, dates of therapy
 - Continuous vs intermittent therapy
- ECOG Performance Status
- Height, Weight
- CBC with differential and platelet count.
- PT or INR, PTT
- Electrolytes, BUN, Creatinine
- Total protein, albumin, calcium, total bilirubin, AST, ALT, LDH
- PSA
- PSA DT Calculation

- Alkaline phosphatase
- Testosterone
- Human anti-J591 antibody sample (may also be drawn C1D1 prior to initiation of study drugs)
- Urinalysis
- Archival Tissue (section 9.1.4) - Paraffin-embedded tumor blocks or 5 unstained slides with representative tumor tissue
- EKG, up to 1 month prior to treatment
- CT or MRI (abdomen-pelvis), up to 4 weeks prior to enrollment
- Bone scan, up to 4 weeks prior to enrollment
 - Any confirmatory tests to assess equivocal results of bone scan should also be completed within 4 weeks of enrollment
 - CXR, up to 4 weeks prior to enrollment (if CT chest has been performed within 4 weeks of enrollment, this procedure is waived)

Evaluations and procedures at Visit 2 (C1D1) – All subjects

Following screening procedures, eligible patients will be dosed with ketoconazole and hydrocortisone. See Section 5.1 for details on the dose and administration.

The following assessments are to be collected prior to drug administration unless otherwise noted:

- Interval medical history
- Targeted Physical Examination with vital signs
- ECOG PS
- CBC with differential and platelet count*
- Electrolytes, BUN, Creatinine*
- PSA*
- Adrenal hormone levels
- Plasma markers
- CTC's
- Adverse Events

- Concomitant medications
- Concomitant procedures
- FACT-P questionnaire (prior to ketoconazole/hydrocortisone administration)
- Ketoconazole/hydrocortisone administration instruction (re-inforcement) – prescriptions should have been filled prior to this visit, but no drugs should have been taken prior to blood draw D1
 - Distribute Medication Diary

*Note that treatment day labs are used for baseline (not for assessment of eligibility), though subjects may be withdrawn from the study for safety concerns per the investigator's discretion.

Phone Assessment (Cycle 1, Day 15 +/- 2 days) – All subjects

- Compliance
- Toxicity screening
- Next visit reminder (confirmation of date/time of next visit with J591 infusion should also be confirmed after delivery date of drug is confirmed)

Evaluations and procedures at Visit 3 (C2D1) – All subjects

Following assessment, eligible, randomized patients who have not come off trial for toxicity or noncompliance will be dosed with radiolabeled-J591. See section 5.2.3 for details on the administration.

Note: The J591 infusion days should be scheduled on a Thursday or Friday. If needed, visits can be scheduled on a Wednesday afternoon but the earliest the site will receive drug is Wednesday at noon. Because of the nature of study drug and shipping, dosing outside of specified window should be discussed with WCMC, but will not require a protocol exception provided the date has been pre-approved by WCMC. The exact date of the J591 infusion will be confirmed 2 weeks prior. The site is not responsible for ordering the J591. WCMC will handle ordering and shipping the drug. The shipping material needs to be sent back to WCMC. A return air bill will be included with the shipment.

Note: In the event that the J591 infusion is delayed, cycle 1 will be extended. The date of the J591 infusion will be considered cycle 2, day 1.

Patients will remain at the clinical site for a minimum of 2 hours after completion of radiolabeled-J591 administration to monitor vital signs. The patient should be considered clinically stable by the investigator prior to discharge. The following assessments are to be collected prior to drug administration unless otherwise noted:

- Interval medical history

- Targeted Physical Examination
- ECOG Performance Status
- Vital Signs (pre-infusion, post infusion as per Section 5.1.3.3)
- Verification of ketoconazole/hydrocortisone administration, Collection/Distribution of diary
- CBC with differential and platelet count*
- Electrolytes, BUN, Creatinine*
- PSA*
- Total protein, albumin, calcium, total bilirubin, AST, ALT, LDH
- Alkaline phosphatase
- Plasma markers
- Adrenal hormones
- CTC's
- Concomitant medications
- Concomitant/interval procedures
- Adverse events (pre- and post- infusion)

*Note that treatment day labs are used for radiolabeled-J591 baseline (not for assessment of eligibility)

Evaluations and procedures at Visit 4/J591 Scan (C2D3-9)

- Adverse Events
- Concomitant medications
- Concomitant/interval procedures
- J591 imaging (2-8 days after infusion). At selected study sites, whole body planar radionuclide images will be obtained between 2-8 days post-J591 treatment. The date of scan (3 or 4 days vs 6-8 days after J591 infusion) will be assigned at the time of randomization. SPECT studies of sites of disease will be obtained in selected patients as appropriate. These will be used to assess the ability of radiolabeled J591 to image

metastatic sites that do not appear on conventional imaging modalities (bone scan, CT/MRI).

Evaluations and procedures C2D22 (safety CBC for some subjects)

For subjects on aspirin/NSAIDs with anti-platelet properties or anticoagulation, a CBC on approximately Day 50 is **required** (3 weeks +/- 2 days after radiolabeled J591 infusion). For all other subjects, in particular subjects with baseline platelet counts < 200/mm³ a CBC at this timepoint is suggested, but not required.

- CBC with differential †

Evaluations and procedures C3D1

- Interval medical history
- Targeted Physical Examination
- Vital Signs
- ECOG Performance Status
- Verification of ketoconazole/hydrocortisone administration, Collection/Distribution of diary
- Adverse Events
- Concomitant medications
- Concomitant/interval procedures
- CBC with differential and platelet count.
- Electrolytes, BUN, Creatinine
- Total protein, albumin, calcium
- Total bilirubin, AST, ALT, alkaline phosphatase, LDH
- PSA
- Plasma markers
- CTCs

Evaluations and procedures Cycle 3 D8 *†

- CBC with differential and platelet count

Evaluations and procedures Cycle 3 D15 *†

- CBC with differential and platelet count†

Evaluations and procedures Cycle 3 D22 *†

- CBC with differential and platelet count†

All CBC results during cycle 3 must be either entered into the REDCap eCRF database or emailed to [contact] within 24 hours of testing.

***Lu-J591 subjects with platelets < 25,000 and/or ANC < 500 are required to have CBC's performed at least twice per week until recovery to platelets > 25,000 and ANC > 500**

† Lu-J591 CBC evaluations may be performed at approved CLIA certified local laboratories with PI's pre-approval

Evaluations and procedures C4D1 – ALL PTS

- Adverse events
- Concomitant medications
- Concomitant/interval procedures
- Verification of ketoconazole/hydrocortisone administration, Collection/Distribution of diary
- Interval Medical History
- Targeted Physical Exam
- Vital Signs
- ECOG Performance Status
- Weight
- CBC with differential and platelet count.
- Electrolytes, BUN, Creatinine

- Total protein, albumin, calcium, total bilirubin, AST, ALT, LDH
- PSA
- Alkaline phosphatase

J591 subjects who have not yet recovered ANC > 1.5 and/or platelet counts > 150 by Visit 9 (Cycle 4 D1) will continue to have CBC's checked weekly until these criteria satisfied or until permission is granted by the Study Chair

Evaluations and procedures q4 weeks while on ketoconazole and until resolution of study drug toxicities with the exception of anemia until EOS

- Adverse events
- Concomitant medications
- Concomitant/interval procedures
- Verification of ketoconazole/hydrocortisone administration, Collection/Distribution of diary
- Interval Medical History
- Targeted Physical Exam
- Vital Signs
- ECOG Performance Status
- Weight
- CBC with differential and platelet count.
- Electrolytes, BUN, Creatinine
- Total protein, albumin, calcium, total bilirubin, AST, ALT, LDH
- PSA
- Alkaline phosphatase
- Other laboratory assessments and procedures as clinically indicated.

NOTE: For individual subjects deemed to be tolerating ketoconazole well, following 6 months on study (after scans) study evaluations need to be performed by official study investigators at official study sites only every 12 weeks. For those subjects who are

tolerating study drug well (in the opinion of the investigator) and for whom travel is a burden, the other two q4 week evaluations may be performed by a local lab with either local physician and/or phone assessment for adverse events (i.e. at least every third visit must be done on site by official study investigators). In this case, source documents should be collected and drug diaries may be collected by fax/mail/email. Subjects who discontinue ketoconazole for any reason may be followed every 12 weeks following resolution of ketoconazole and study drug toxicities (except anemia).

Radiographic Evaluation and Patient Reported Outcome Evaluation

- Bone scan, CT/MRI abdomen/pelvis, and CXR + FACT-P[#] at baseline
- Bone scan*, CT/MRI of abdomen/pelvis, and CXR + FACT-P[#] will be repeated every 6 months in the absence of biochemical or clinical progression
- Bone scan*, CT/MRI of abdomen/pelvis, and CXR + FACT-P[#] will be repeated every 3 months subsequent to biochemical or clinical progression
- In addition, a bone scan will be performed for subjects with clinical signs or symptoms of bone metastases at the investigators discretion

*During the first 6 months, bone scan progression requires confirmation by a 2nd bone scan. The date of progression is defined as the date of the 1st scan that is subsequently confirmed to be positive.

[#]FACT-P to be administered either prior to imaging or following imaging, but before results of scans are disclosed to subject.

Evaluations and procedures at PSA progression

Note: subjects may remain on ketoconazole/hydrocortisone beyond PSA progression at the discretion of the investigator and/or their treating physician

- Adverse events
- Concomitant medications
- Concomitant/interval procedures
- Verification of ketoconazole/hydrocortisone administration, Collection of diary
- Interval Medical History
- Complete Physical Exam
- Vital Signs
- ECOG Performance Status

- Weight
- CBC with differential and platelet count.
- Electrolytes, BUN, Creatinine
- Total protein, albumin, calcium, total bilirubin, AST, ALT, LDH
- Alkaline phosphatase
- PSA
- Testosterone
- Plasma markers
- CTC's
- Adrenal hormones
- Other laboratory assessments and procedures as clinically indicated.
- FACT-P

Evaluations and procedures at End of Study (EOS = development of metastatic disease on scans)

Note: subjects may remain on protocol past initial scans with evidence of metastatic disease if confirmatory scans are warranted

- Adverse events
- Concomitant medications
- Concomitant/interval procedures
- Verification of keto/hydrocortisone administration, Collection of diary (if relevant)
- Interval Medical History
- Complete Physical Exam
- Vital Signs
- ECOG Performance Status
- Weight

- CBC with differential and platelet count.
- Electrolytes, BUN, Creatinine
- Total protein, albumin, calcium, total bilirubin, AST, ALT, LDH
- Alkaline phosphatase
- PSA
- Testosterone
- Plasma markers
- CTC's
- Human anti-J591 antibody sample
- Other laboratory assessments and procedures as clinically indicated.
- FACT-P

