5.2.1 Excluded medications

- Aspirin and/or non-steroidal anti-inflammatory agents possessing anti-platelet activity must be discontinued if the platelet count drops below 150,000. These medicines may be re-initiated at the discretion of the treating physician after confirmed recovery from any thrombocytopenia (after 2 consecutive rises with $2^{\text{nd}} \geq 100,000$).
- Anti-platelet medications including, but not limited to, abciximab, cilostazol, clopidogrel, dipyridamole and ticlopidine HCL should be discontinued be discontinued if the platelet count drops below 150,000. These medicines may be re-initiated at the discretion of the treating physician after confirmed recovery from any thrombocytopenia (after 2 consecutive rises with $2^{\text{nd}} \geq 100,000$).
- Anti-coagulant medications including, but not limited to, heparins (unfractionated and low molecular weight forms), coumarins (including warfarin sodium), anti-Xa inhibitors (including fondaparinux and abixaban), and direct thrombin inhibitors (including rivaroxaban) at therapeutic doses when platelet count <50,000/mm³. These medications may be re-initiated

upon confirmed recovery of thrombocytopenia (after 2 consecutive rises with the 2nd above 75,000)

- Any investigational mAb based therapy not covered in this protocol. Note that “approved” monoclonal antibody therapy such as denosumab is allowed provided that subjects have initiated therapy and are on a stable dose/schedule at least 1 month prior to enrollment.
- Medication to support platelet count (such as oprelvekin (Neumega®), romiplostim (Nplate), eltrombopag (Promacta)).
- Patients on drugs known to be metabolized by the cytochrome P450 system (specifically CYP 3A4) should be cautioned about potential interactions with ketoconazole. Specifically, cisapride, terfanadine and astemizole are contraindicated (see black box warning in product’s label). Any such interactions should be discussed with the patient’s treating physician.

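### The required week-3 platelet check after the J591 infusion leaves out men taking only a clopidogrel-type drug, though that class has the same 150,000 stop level as aspirin and NSAIDs

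*Combined protocol and SAP*

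**What the plan says.** Section 5.2.1 treats three drug classes in separate bullets:

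- Aspirin and NSAIDs: "Aspirin and/or non-steroidal anti-inflammatory agents possessing anti-platelet activity must be discontinued if the platelet count drops below 150,000".
- Clopidogrel-type drugs: "Anti-platelet medications including, but not limited to, abciximab, cilostazol, clopidogrel, dipyridamole and ticlopidine HCL should be discontinued", again below 150,000.
- Anticoagulants are excluded "at therapeutic doses when platelet count <50,000/mm³", a much lower level.

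The safety blood count at C2D22 is set out in two places. Section 10.1 says "For subjects on aspirin/NSAIDs with anti-platelet properties or anticoagulation, a CBC on approximately Day 50 is" required; for all other subjects, and particularly those with low baseline platelets, "a CBC at this timepoint is suggested, but not required". The footnote to the section 10 calendar is shorter: "CBC on D50 +/- 2 days is required for pts on anticoagulation or NSAIDS, suggested in pts with baseline plt count < 200". Neither text names the clopidogrel-type drugs in the required group.

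Counts are required at screening, C1D1 and C2D1 (the infusion day). None is listed at the C2D3-9 imaging visit. Counts resume at C3D1 and are then weekly through cycle 3, with results reported within 24 hours. Section 5.2.2.1 places the platelet nadir 4 to 5 weeks after infusion and requires twice-weekly counts while platelets are below 25,000.

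**The concern.** A stop rule triggered by platelets works only if platelets are measured. The plan requires a week-3 count for men on drugs that raise bleeding risk. It includes the class with the 50,000 limit and omits one of the two classes with the 150,000 limit, without giving a reason. Because 5.2.1 lists clopidogrel-type drugs apart from both aspirin/NSAIDs and anticoagulants, the required group in 10.1 cannot fairly be read to include them.

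At stake is the safety of a small group. Exclusion 3.2.6 admits men at 150,000 or above, so a man who enters close to that floor needs only a small fall to reach the stop level. Deep falls are expected with this agent: in the phase II trial described in section 2.1, 42% of men had a nadir below 25 x 10^9/L. The twice-weekly rule does not close the gap, because it applies only once a very low count has been found. No endpoint or efficacy analysis is affected.

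**Working it through.** **Inputs**

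- Infusion day: section 8.2 refers to the "proposed D29 radiolabeled J591 infusion date", so C2D1 is day 29. If the infusion is delayed, its date becomes C2D1 (section 10.1), so the intervals below still hold.
- C2D22 count: 3 weeks after infusion, plus or minus 2 days (section 10.1).
- Visit window: plus or minus 3 days through Visit 9, day 85 (section 10.1).
- Expected nadir: 4 to 5 weeks (section 5.2.2.1), which is days 28 to 35 after infusion.
- Sample size 55, allocated 2:1 (sections 13.1 and 13.2).

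**Reproducing the plan's own days**

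- C2D22 = 29 + 21 = day 50, as stated.
- C3D1 = 29 + 28 = day 57, and C4D1 = 57 + 28 = day 85, which matches the stated day for Visit 9. Cycles are therefore 28 days.

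**First required count after infusion**

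| Only relevant drug | First required count | Days after infusion | Window |
|---|---|---|---|
| Aspirin/NSAID or anticoagulant | C2D22 | 50 - 29 = 21 | 19 to 23 |
| Clopidogrel type | C3D1 | 57 - 29 = 28 | 25 to 31 |

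The difference is 28 - 21 = 7 days. Pairing opposite ends of the windows gives 25 - 23 = 2 days at least and 31 - 19 = 12 at most; 7 is the figure to use. The covered men are checked before the expected nadir. For the others, the first required count falls around its start.

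**Number of men**

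- 177Lu-J591 arm: 55 x 2/3 = 36.7, about 37.
- The documents do not say how many take a clopidogrel-type drug alone. Assuming 2% to 10%: 36.7 x 0.02 = 0.7 and 36.7 x 0.10 = 3.7, or about 1 to 4 men.
- At the phase II rate, those with a nadir below 25 x 10^9/L would number 0.7 x 0.42 = 0.3 to 3.7 x 0.42 = 1.5. This shows how serious the falls can be; it does not measure what the fix would gain. The 42% pools the 65 and 70 mCi/m² cohorts in metastatic disease, and section 12.4 expects toxicity here not to exceed that experience.

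**Footnote against section 10.1**

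The footnote does not name aspirin, and it suggests the count only when baseline platelets are below 200. Section 10.1 names aspirin and suggests the count for everyone else. A site working from the calendar would see no prompt at all for a man on clopidogrel with baseline platelets of 210.

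**The case against.** The strongest reply is that these men are largely covered already. Section 10.1 suggests the count for them at the same visit, three counts are required up to and including the infusion day, and weekly counts begin at C3D1, when the nadir is only starting. This stands, and it is why the benefit is small. A suggested test can still be skipped without a deviation, and the calendar footnote does not even suggest it for men with baseline platelets of 200 or more.

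A second reply is that a day-21 count may come too soon to show a fall below 150,000. Section 5.2.2.1 asks physicians to look for other causes of falls outside a stated period; its wording is unclear, but it may mean that little drug-related fall is expected before week 3. The documents give no day-21 counts, so this cannot be settled. A man still above 150,000 at that visit gains nothing.

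Third, 5.2.1 uses mandatory wording for aspirin and NSAIDs and advisory wording for clopidogrel-type drugs, so a required test for one and a suggested test for the other could be deliberate. The plan does not say so, and the trigger level is the same. Anticoagulant users may merit an early count for bleeding risk whatever their stop level, so that comparison alone does not prove an error.

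Finally, 5.2.1 lets these drugs restart once a second consecutive rise reaches 100,000, so 150,000 is not treated as a point of acute danger. That lowers the urgency, although a recovering count is not the same as a falling one.

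**Conclusion.** The concern holds. For men whose only relevant drug is of the clopidogrel type, the plan has a stop level of 150,000 but requires no count between C2D1 and C3D1. Their first required count after infusion is at day 28 (window 25 to 31), 7 days later than for aspirin/NSAID or anticoagulant users. The omission and the timing follow directly from the text.

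The clinical size is less certain and probably small: about 1 to 4 men in the 177Lu-J591 arm, on an assumed 2% to 10% use that the documents do not supply. The gain is in the date of the test. Whether the drug would be stopped sooner depends on day-21 counts that are not given. The change is worth making as an inexpensive safety improvement.

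**What to change.** In the C2D22 paragraph of section 10.1 and in the calendar footnote of section 10, add the anti-platelet drugs listed in 5.2.1 to the group for whom the day-50 count is required. In the same edit, bring the footnote into line with 10.1: name aspirin in the required group, and suggest the count for all other subjects.

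The cost is a wording change in one paragraph and one footnote. One blood count that 10.1 already suggests, and that a CLIA-certified local laboratory may perform, becomes mandatory for a few men. The trial is double-blind, so this applies in both arms: on the same assumption, 55 x 0.02 = 1.1 to 55 x 0.10 = 5.5 men. Randomization, blinding and endpoints are unchanged.
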